Body temperature is one of the most frequently studied physiological variables in hospitalized patients. The normal temperature value is around 36.7°C, with significant variability ranging from 35.3 to 37.7°C among different individuals or within the same person throughout the day. The definition of fever is established by a consensus reached by the American College of Critical Care Medicine and the IDSA, placing it at a central temperature of 38.3°C (1), where central temperature refers to the temperature of internal organs. This thermal elevation is typically found in approximately 50% of critical patients (2) and is not only clearly associated with infectious processes but can also be observed in various other conditions such as autoimmune diseases, oncological conditions, bleeding, inflammatory reactions, after surgical procedures, or drug-induced (3).

There are multiple methods for temperature measurement in Intensive Care Units (ICUs), with the most common being peripheral temperature measurement every eight hours using contact thermometers in the axilla(4). In patients with sustained fever or those undergoing therapeutic hypothermia, continuous monitoring of central temperature through rectal, tympanic, vesical, or esophageal methods can be performed (5). However, it is considered a more invasive measure, and its use is limited mainly due to technical difficulties, higher economic costs, and potential serious complications (6, 7).

Thermal monitoring in critical patients is essential. Many critical patients with fever will receive antibiotic treatment, even in the absence of evidence of infection, as early initiation of this treatment in septic patients clearly improves survival (8, 9).

The wide variability of temperature between individuals, circadian changes, different methods of temperature measurement, the influence of medications, and deficiencies in measurement methods make defining fever with a single temperature value impractical (10) Therefore, other patient variables should also be considered before establishing the presence of fever. One of these variables is the thermal curve, or the evolution of temperature throughout the day, which can be sustained or in peaks and may or may not respond to antipyretics, antibiotics, or other temperature control methods. Studying a patient's thermal curve is useful even before reaching definitive fever values (11).

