- Patients who provide voluntary consent to participate in the study (Annex 2). If the participant is not in full physical or intellectual capacity to provide their signature in the informed consent, the responsible investigator will seek consent from their direct family member or the legally designated person to make decisions on their behalf regarding health matters. This measure is adopted to ensure the participant's rights are respected and the integrity of the consent process is maintained, even in situations where their decision-making capacity may be compromised.

Exclusion Criteria:

Patients from whom information from the thermal imaging camera cannot be obtained due to technical reasons.

Sample Size:

To determine the degree of concordance between the temperature recorded by the thermal camera and axillary temperature, a minimum of 224 pairs of data (224 temperature records by thermal camera vs. 224 axillary temperature records) will be required to estimate an Intraclass

Correlation Coefficient (expected to be 0.8 or higher) with an estimation error of +- 0.05 points, a confidence level of 95%, and anticipating a 10% loss.

Data Collection:

Temperature measurements will be autonomously recorded by the SF-HANDHELD-80TA05 thermal imaging camera, or another with similar characteristics, which provides temperature values every second, thermal images, bed number, date, and time.

The rest of the variables needed for the study will be manually collected by the researchers or through the clinical information system (CIS) "Innovian" and included in a study-dedicated database hosted on the hospital intranet.

Finally, all data will be collected in a pseudonymized manner. For this purpose, two databases will be constructed. One will contain personal data associated with a code (one for each patient), which will be safeguarded by the investigator. The second database will contain the associated clinical data. In the case of images generated by thermal cameras, these will also be pseudonymized, generating images with the aforementioned association code. These coded images will be sent to the Computing Center of the European University of Madrid for the creation of temperature patterns (secondary objectives 4 and 5) and for the adequacy of regional thermal measurement (secondary objective 6).

Standard Practice in Peripheral Temperature Measurement in Our Unit

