The standard practice for peripheral temperature measurement in the ICU at HLA Moncloa University Hospital is not formally documented but adheres to recommendations for monitoring temperature in critically ill patients. Peripheral temperature is obtained using a contact thermometer in the axilla every 8 hours or whenever thermal disturbances are suspected by healthcare personnel (both medical and nursing staff).

Axillary temperature measurement through standard practice will be repeated every 8 hours and collected in triplicate to establish an average used for assessing concordance at that point and so forth until reaching the 224 measurements needed to complete the primary objective of the study. If, during the 8-hour collection, there is a difference of more than 15% between the first 3 measurements, a fourth measurement will be taken, and only the average of the three most similar measurements will be used for concordance. If all four measurements are different, a fifth measurement will be taken, and so on until three measurements considered similar are obtained.

Definitions of Thermal Disturbances and Infectious Complications:

- Fever: Defined as a central temperature (rectal, esophageal, vesical, or tympanic) $\geq 38.3^{\circ}\text{C}$. Peripheral temperature (cutaneous or axillary) is 0.6 to 1°C lower than central temperature; therefore, for this study, we will consider a peripheral temperature $\geq 37.5^{\circ}\text{C}$ as a fever.
- Hypothermia: Defined as a central temperature $< 35^{\circ}\text{C}$ or peripheral temperature $< 34.2^{\circ}\text{C}$.
- Infectious Complications: Will include both patients admitted to the ICU due to an infection (pre-admission infection) and patients who develop an infection during their stay in the ICU (infection during admission). Identification and diagnosis of either type of infection will be

carried out by the attending physician following established clinical practice recommendations and guidelines in each specific case. The task of the researchers will be limited to reviewing the patient's medical history and collecting data.

Temporal Differences in Fever Detection:

The time of fever detection will be identified for each measurement method (standard practice vs. thermal imaging camera), and the temporal difference in minutes between them will be determined.

Creation of Temperature Patterns:

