Continuous temperature data (every second) offered by thermal cameras will be represented by 24-hour thermal curves and classified automatically based on patterns and patient characteristics using unsupervised machine learning algorithms such as clustering. For this purpose, the data will be physically and securely sent to the Computing Center of the European University of Madrid.

Adequacy of Regional Thermal Measurement:

Thermal cameras SF-HANDHELD-80TA05 or similar perform a scan across the entire thermal image to extract the point of maximum temperature found. It is deemed necessary for the study to visually check the thermal images obtained to verify the adequacy of temperature measurement—ensuring that the temperature is being obtained from the patient and not from any other high-temperature element, such as healthcare personnel or electronic devices (mobile phones, respirators, pumps, etc.). A direct visual check of a sample of thermal images will be performed by the researchers, and all thermal images will be physically and securely sent to the Computing Center of the European University of Madrid for automatic classification using convolutional image recognition algorithms (machine learning) to identify whether the temperature is obtained from the patient or any other element.

Interventions and Procedures:

1. All patients admitted to the ICU in a room with a thermal imaging camera will be considered potential candidates for inclusion in the study and will be verbally informed and provided with patient information sheets about the study, requesting their signature on the informed consent form for participation.
2. If they agree to participate, compliance with inclusion and exclusion criteria will be confirmed.
3. Patients will receive treatments according to the center's usual clinical practice and the criteria of their attending physician based on the patient's characteristics in each specific case.
4. The thermal imaging camera will automatically record temperature readings every second and capture a thermal image. The information will be recorded in real-time on

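### Objective 3 times camera fever detection from a whole-image maximum that may not be the patient's, and nothing carries the planned image classification into that timing

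*Protocol*

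**What the plan says.** The method for secondary objective 3 is one sentence, found in the Protocol's section Temporal Differences in Fever Detection. It reads: "The time of fever detection will be identified for each measurement method (standard practice vs. thermal imaging camera), and the temporal difference in minutes" is then determined. It sets no condition on where the camera reading comes from and does not define detection.

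The only criterion that could serve for the camera is in Definitions of Thermal Disturbances and Infectious Complications: "Peripheral temperature (cutaneous or axillary) is 0.6 to 1°C lower than central temperature; therefore, for this study, we will consider a peripheral temperature" of 37.5°C or more to be fever.

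Under Adequacy of Regional Thermal Measurement, the cameras "perform a scan across the entire thermal image to extract the point of maximum temperature found". The same section calls for a check that the value comes from the patient and "not from any other high-temperature element, such as healthcare personnel or electronic devices". Researchers view a sample of images, and an algorithm classifies all of them "to identify whether the temperature is obtained from the patient or any other element".

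Under Data Collection, the coded images go to the computing centre "for the creation of temperature patterns (secondary objectives 4 and 5) and for the adequacy of regional thermal measurement (secondary objective 6"). Objective 3 is not in that list. The section titled Statistical Analysis Plan does not mention objective 3 either. The only exclusion criterion concerns patients for whom no camera information can be obtained. It does not act on single readings.

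**The concern.** Followed as written, objective 3 uses values whose source the Protocol itself doubts, although the work that would identify the doubtful ones is already planned. The reported lead would then mix the real gain from continuous monitoring with crossings that are not the patient's.

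The result would not show this by itself. The background text notes that sporadic measurement can miss febrile peaks, and a missed peak gives a long lead that is genuine. Without the classification, genuine and false long leads look alike. The time gained could be used to support the change in ICU temperature monitoring that the background text foresees.

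**Working it through.** Objective 3 has no planned figure to reproduce. The 224 pairs belong to the primary objective and do not bear on this point.

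**Direction.** Within any image, the image maximum is at least the patient's own maximum. Under a first-crossing rule, the image maximum therefore reaches 37.5°C no later than the patient does. This needs no assumed rate, but it covers only fevers that the camera does see.

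**Inputs from the Protocol.** Axillary rounds are every 8 hours (480 minutes), the cut-off is 37.5°C, and the camera gives one value per second.

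**Assumptions.** Non-patient episodes occur at random at 0.1, 0.5 or 1 per day (the Protocol gives no rate). Onset is uniform over H minutes. The camera otherwise detects at onset. Fever lasts to the next round, and there are no extra axillary readings on suspicion.

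**Real lead.** The delay from onset to the next round is uniform on 0–480 minutes, so its mean is 480/2 = 240.

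**Added lead.** With L = episodes per day/1,440 and a = L × H:

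added mean = ∫₀ᴴ (H − t)²/(2H) · L·e^(−Lt) dt = H × [1/2 − 1/a + (1 − e^(−a))/a²]

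share with a non-patient crossing before onset = 1 − (1 − e^(−a))/a

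Example, H = 1,440 and 0.5 per day: a = 0.5, and 1,440 × (0.5 − 2 + 0.39347/0.25) = 1,440 × 0.07388 = 106.4 minutes.

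| Onset within | Episodes per day | Added mean (min) | Apparent mean lead (min) | Share crossing early |
|---|---|---|---|---|
| 24 h | 0.1 | 23.4 | 263 | 0.048 |
| 24 h | 0.5 | 106.4 | 346 | 0.213 |
| 24 h | 1 | 190.3 | 430 | 0.368 |
| 72 h | 0.1 | 200.7 | 441 | 0.136 |
| 72 h | 0.5 | 771.6 | 1,012 | 0.482 |
| 72 h | 1 | 1,176.1 | 1,416 | 0.683 |

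The Protocol summarises non-normal data by the median. In 2,000,000 simulated patients with onset over 72 hours, the median moves from 240 to about 275, 432 and 1,090 minutes.

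**Look-back limit.** If only crossings shortly before axillary detection count (same simulation, 72-hour onset), the mean lead at 0.1, 0.5 and 1 per day is 243, 252 and 263 minutes for an 8-hour look-back. For 24 hours it is 280, 420 and 557.

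**When the camera misses fevers.** Assume a 7-day stay, onset over 72 hours, and that a missed fever enters the comparison only through a non-patient crossing. With 30% of fevers missed and 0.1 episodes per day, the mean lead among paired patients falls to about zero (−1 to −4 minutes across simulation runs). With 50% missed it is about −395. With 30% missed and 0.5 or 1 per day it is about 670 or 1,280. The sign therefore depends on the episode rate and on camera sensitivity, and the Protocol gives neither.

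**The case against.** **Left to an analysis plan.** Artefact handling and an operational detection rule are often placed in a separate analysis plan, and the Protocol does not state first crossing. This stands in part, and it lowers the severity. But the Protocol itself says that the camera value may not be the patient's, and where it lists the uses of the image work it leaves objective 3 out. That is more than missing routine detail.

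**Intent to verify.** The image check is described as necessary for the study and aimed at making sure that the patient is the source. The list of objectives under Data Collection may only explain why images leave the hospital. A reader might infer from that list that the investigators mean to keep non-patient readings. The text does not support this: it shows intent to check and does not say what happens to a reading that fails. The primary objective and objective 2 use the same camera value and are not listed either, so the remedy should cover them.

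**Staff may not reach the cut-off.** The background text says "The normal temperature value is around 36.7°C" with a range up to 37.7°C. If these are central values, subtracting the Protocol's 0.6 to 1°C gives 35.7–36.1°C peripherally, and at most 37.7 − 0.6 = 37.1°C. Both are below 37.5°C, so afebrile staff would rarely cross and devices would be the main source. A device constantly in view would give a persistent crossing, not the sporadic episodes modelled. This is fair, and it is one reason why the sizes are only illustrative.

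**Extra axillary readings.** Staff also measure on suspicion, which shortens the real lead below 240 minutes. This stands.

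**Conclusion.** The point holds as a gap with a conditional bias. Objective 3 takes its camera time from a value that may not be the patient's, and no provision applies the planned classification to it. Under first crossing, a non-patient reading before onset can only inflate the lead.

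Two stronger readings are tempting and are not supported. One is that the error always favours the camera. It does not if the camera misses fevers and later non-patient crossings are paired with them. The other is that the lead is overstated by many hours. The added mean runs from about 3 minutes (8-hour look-back, 0.1 per day) to 1,176 minutes (72-hour onset, no look-back limit, 1 per day). All of it rests on assumed rates, an assumed onset window, first crossing, and camera detection at onset.

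Severity is minor to moderate: this is a descriptive secondary objective, and the rule can still be set before analysis.

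**What to change.** - State that readings whose image is classed as non-patient are set to missing before camera fever detection is timed. Apply the same rule to the other analyses of the camera value: the primary ICC and objective 2. Linking is feasible in principle, because the camera "which provides temperature values every second, thermal images, bed number, date, and time".
- Fix the camera detection rule, using the existing cut-off, before the data are analysed. A smoothing window is optional.
- Report objective 3 with and without the exclusion. Give classifier accuracy against the sample checked by eye, and the counts of camera-only and axilla-only detections beside the time difference in patients detected by both.

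**Cost.** The change is a few sentences, since the classification and the visual check are already planned. Objective 3 must wait for the classification, because images are sent only after the 11-month collection ends. The image capture rate is not clearly stated, so readings without a matching image would be lost. The result also depends on classifier accuracy. If 10% of episodes escape at a true rate of 1 per day, the residual rate is 0.1 per day, and the 0.1 rows of the table apply: 23 minutes still added for onset within 24 hours, 201 for 72 hours.

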the server dedicated to the study, located physically within the ICU and connected only to the hospital intranet. This ensures that the information collected for the study has the same level of security as other information related to hospitalized patients. Additionally, all records made on the server will be pseudonymized from personal information. Identifying a person through the thermal image is not possible without additional information; thus, for all intents and purposes, it is considered anonymized information.

[figure not shown]

Figure 1. Example of Thermal Image

5. Temperature data for each patient included in the study can be accessed through a tablet connected only to the hospital intranet and will remain within the ICU.
6. At the time of discharge or patient exitus, the principal investigator will review the patient's medical history to create a pseudonymized database that records study variables and patient temperature data.
7. Once data collection is complete over the 11-month study period, the principal investigator will physically send pseudonymized temperature data and thermal images to the Computing Center of the European University of Madrid, which is committed to maintaining data confidentiality and destroying any possible copies of the material once study objectives are fulfilled.
8. After completing the study, pseudonymized patient data will remain recorded for 5 years on the server physically located within the ICU. This is in case data consultation is necessary for clinical reasons or regarding the publication of study data.

Variables

Primary:

- Axillary Temperature
- Temperature from Thermal Imaging Camera

Secondary:

- Age
- Gender
- Reason for Admission:
 - Altered Level of Consciousness and Other Neurological Disorders
 - Acute Coronary Syndrome
 - Cardiac Arrhythmias
 - Cardiorespiratory Arrest
 - Heart Failure/Cardiogenic Shock

- Hypovolemic Shock
- Sepsis/Septic Shock
- Shock of Other Etiology
- Respiratory Failure
- Renal Failure and Metabolic Disorders
- Intoxications
- Head Trauma
- Other Traumas without Head Injury
- Postoperative Monitoring and Surveillance
- Monitoring and Surveillance of Non-Surgical Procedures
- Other Unspecified Medical or Surgical Conditions
- Hypertension (Yes/No)
- Diabetes Mellitus (Yes/No)
- Dyslipidemia (Yes/No)
- SAPS3 at Admission
- Thermal Image
- Fever (Yes/No)
- Hypothermia (Yes/No)
- Infectious Complications (Pre-existing or During Admission) Date and Time

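### The camera reading is the hottest point in the whole image, and neither planned check that this point is the patient is linked to the ICC or the fever and hypothermia accuracy analyses

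*Protocol*

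**What the plan says.** Under Adequacy of Regional Thermal Measurement, the protocol states that the cameras "perform a scan across the entire thermal image to extract the point of maximum temperature found". The same paragraph calls a check of the images necessary, with the aim of "ensuring that the temperature is being obtained from the patient and not from any other high-temperature element", and names staff and electronic equipment as examples.

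Two checks follow:

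- "A direct visual check of a sample of thermal images will be performed by the researchers". The size of the sample, how it is drawn and what follows from a failed check are not given.
- All images go to the university computing centre for "automatic classification using convolutional image recognition algorithms (machine learning) to identify whether the temperature is obtained from the patient or any other element". Under Interventions and Procedures, step 7, they are sent "Once data collection is complete over the 11-month study period".

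Data Collection gives the purpose of this transfer as secondary objectives 4, 5 and 6. Objective 6 is the adequacy of the regional measurement.

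The Statistical Analysis Plan section sets the ICC for the primary objective, and sensitivity, specificity, PPV and NPV for fever and hypothermia. It mentions neither check. The one exclusion criterion is "Patients from whom information from the thermal imaging camera cannot be obtained due to technical reasons", which concerns absent data at patient level. Sample Size asks for "a minimum of 224 pairs of data", based on an expected ICC of 0.8, an error of ±0.05, 95% confidence and 10% loss.

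**The concern.** The protocol identifies a source of error in its primary variable, plans to detect it, and then does not connect the detection to the analyses that the error affects. Nothing in the text removes, marks or separately reports a pair whose camera value came from something other than the patient.

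What is at stake is interpretation. A low ICC could mean that the camera and the axilla disagree on the patient, or that something else was often the hottest object in view. The first counts against the camera as a thermometer. The second points to framing or region selection. The plan as written cannot separate them.

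The paired frames may be more exposed than a typical frame. Each axillary reading is taken by contact thermometer in triplicate, so someone is probably at the bedside at that moment. This is an inference, and the protocol gives no rate.

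**Working it through.** **1. The plan's own figure.** The Bonett precision formula with k = 2 measurements, r = 0.80, full width w = 0.10 and z = 1.96 is

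n = 8z²(1−r)²(1+(k−1)r)² / [k(k−1)w²] + 1 = 8 × 3.8415 × 0.04 × 3.24 / (2 × 0.01) + 1 = 200.1, so 201 pairs.

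With 10% loss, 201/0.9 = 223.3, rounded up to 224. The sample size reproduces and is not in dispute.

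**2. Direction.** If another object is in view, the recorded value is max(patient, object). It is never below the patient's own maximum. False fever readings can be added and true fevers can only be gained. Hypothermia can be masked.

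**3. Size, under assumptions.** The documents give no contamination rate, source temperature or SD. Assumed inputs:

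- True patient temperature is normal with mean 36.7°C (the normal value given in the protocol's introduction) and SD 0.7°C.
- Each method adds independent error with SD 0.35°C, so that 0.49/(0.49 + 0.1225) = 0.80.
- In a fraction p of pairs, camera = max(patient reading, source), with source mean 36, 37 or 38°C and SD 0.4°C.
- The fever cut-off of 37.5°C applies to both methods. About 15% of axillary readings are then febrile.

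The ICC is the two-way, absolute-agreement, single-measure form: (MSR − MSE) / [MSR + (k−1)MSE + (k/n)(MSC − MSE)].

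| Source mean | ICC at p = 0 / 10 / 20 / 30% | Share for a 0.05 fall in ICC | Pairs of 224 |
|---|---|---|---|
| 36°C | 0.80 / 0.79 / 0.79 / 0.78 | 76.3% | 171 |
| 37°C | 0.80 / 0.76 / 0.71 / 0.67 | 11.7% | 26 |
| 38°C | 0.80 / 0.66 / 0.54 / 0.44 | 3.3% | 7 |

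| Fever measure | p = 0 | 36°C, 10% / 30% | 37°C, 10% / 30% | 38°C, 10% / 30% |
|---|---|---|---|---|
| Specificity | 0.93 | 0.93 / 0.93 | 0.92 / 0.90 | 0.85 / 0.68 |
| PPV | 0.61 | 0.61 / 0.61 | 0.58 / 0.53 | 0.43 / 0.29 |
| Sensitivity | 0.61 | 0.61 / 0.61 | 0.62 / 0.62 | 0.65 / 0.72 |
| NPV | 0.93 | 0.93 / 0.93 | 0.93 / 0.93 | 0.93 / 0.93 |

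A separate run with other assumptions (mean 36.5°C, SD 0.6 to 0.8°C) widens the range. A 40°C device in 2% of pairs took the ICC to 0.57–0.65. Staff at patient-like temperatures in 10% of pairs took it only to 0.76.

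No weight is put on hypothermia. Under the main inputs about 0.16 axillary readings below 34.2°C are expected in 224 pairs.

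**4. Precision of a verified subset.** Half-width = ½√[8z²(0.04)(3.24) / (2(n−1))] at ICC 0.80. Flagging 10, 20 or 30% of 224 leaves 202, 179 or 157 pairs, with half-widths of 0.050, 0.053 and 0.056.

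**The case against.** The strongest reply is that the protocol already deals with the hazard. It names it, calls checking necessary and commits to classifying every image, so each paired frame could carry a label. A rule for flagged readings is often left to a separate SAP, and silence is not a wrong rule. Part of this stands: the missing piece is small. But the protocol has its own section headed Statistical Analysis Plan, which sets these analyses on recorded values, while Data Collection directs the image work to other objectives. If the use of the labels is not stated, the choice of pairs is left open until results can be seen.

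The second reply is that as-recorded values are what an automated system delivers, and the primary objective concerns temperature obtained continuously by the camera. This stands. The hypothesis's reference to critical patients may simply name the population. The as-recorded analysis is a legitimate answer and should be kept. On its own, however, it cannot explain a poor result.

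Third, a reader might infer that classification after collection comes too late to be of use. It is too late to replace a pair, but not to exclude or stratify one.

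Fourth, the size is assumed throughout. That is correct, and it limits how strongly the point can be put.

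**Conclusion.** The point holds and should be fixed. By its own account the protocol's primary camera variable may include non-patient readings, and no planned analysis separates them. That gap follows from the text and needs no assumption. Its numerical effect does rest on assumed inputs and runs from negligible (36°C source) to large (38°C source).

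Three stronger readings are not supported. A reader might infer that the flaw could produce false concordance, but in every scenario run the ICC fell, against the study hypothesis. A reader might infer that the as-recorded ICC is invalid, but it answers the stated primary objective. A reader might infer that 224 pairs are too few, but if 10% of pairs are flagged and nothing else is lost, 202 remain against the 201 needed.

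**What to change.** Amend Adequacy of Regional Thermal Measurement so that the sample for the planned visual check includes every camera frame used in a concordance pair (224 under Sample Size), read blind to the axillary value. In the Statistical Analysis Plan section:

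- keep the ICC, sensitivity, specificity, PPV and NPV as recorded, with flagged pairs included, because a verified set alone could flatter the automated system;
- add the same measures restricted to patient-verified pairs;
- state before analysis which set is primary;
- report the number of pairs flagged.

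The cost is about four hours of review by researchers already assigned to it (224 frames at an assumed one minute each = 3.7 hours), plus the modest loss of precision shown in step 4 of the working. No extra pairs are required. Collecting beyond 224 to offset flagged pairs would be optional. It would also need a change to the section on standard practice in temperature measurement, which continues collection only until 224 is reached.
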